7.1.4. Analysis of Safety (Persistence Epoch)

At each persistence time point, all reported SAEs related to vaccination and any event related to lack of vaccine efficacy since the last persistent time point the subject participated in up to each persistence visit in the current study will be described in detail in a retrospective manner.

Listings will be compiled for

- All SAEs
- AEs/SAEs leading to withdrawal
- SAEs related to study vaccination or any event related to lack of vaccine efficacy
- SAEs related to study participation
- Intercurrent medical conditions

for the time interval from last persistence time point subject participated in up to Month 126.

7.2. Post-booster Analyses

7.2.1. Analysis of Demographics/Baseline Characteristics

Demographic characteristics of subjects in each study cohort will be tabulated: age (in years) at booster vaccination (with the range and standard deviation), sex, and geographic ancestry.

The distribution of subjects among the study sites will be tabulated as a whole and per group.

7.2.2. Analysis of Postbooster Immunogenicity

The analysis of postbooster immunogenicity for MenC will be based on the booster ATP cohort for immunogenicity - MenC.

The analysis of postbooster immunogenicity for MenA, MenW-135, and MenY will be based on the booster ATP cohort for immunogenicity - MenAWY.

MenACWY-TT-100 (C0921004)

If, for any vaccine group, the percentage of subjects who have at least 1 serological result but are also excluded from the booster ATP cohort is higher than 10%, a second analysis based on the booster total vaccinated cohort will be performed to complement the booster ATP analysis.

7.2.2.1. Within Group Analysis

For each vaccine group, at each blood sampling time point (Month 126 and Month 127), for each antigen assessed:

- GMTs with 95% CIs will be tabulated.
- Percentages of subjects with titers above proposed cutoffs and vaccine response with 95% CIs will be calculated.
- The antibody titers will be tabulated and also presented using reverse cumulative distribution curves.

MenACWY-TT-100 (C0921004)

7.2.3. Analysis of Post-booster Safety

The safety analysis will be performed on the booster total vaccinated cohort. If more than 10% of the enrolled subjects are excluded from the booster ATP cohort for safety, all analyses will be performed on the booster ATP cohort for safety to support the analyses of the booster total vaccinated cohort.

For each vaccine group, after the booster vaccination administered at Visit 5:

The number and percentages of subjects with at least 1 local event (solicited event and unsolicited AE), with at least 1 general event (solicited event and unsolicited AE) and with any event during the 4-day (Days 0-3) follow-up period will be tabulated with exact 95% CI. The same calculations will be performed for events rated as Grade 3 and for events related to vaccination.

The numbers and percentages of subjects reporting each solicited local (any grade, Grade 3, medical advice) and general (any grade, Grade 3, related, Grade 3 and related, medical advice) event during the 4-day follow-up period (Days 0-3) after vaccination and their exact 95% CIs will be tabulated. Occurrence of fever will also be reported to 0.5°C cumulative increment as well as the percentage of subjects with oral temperature >39.5°C.

The verbatim reports of unsolicited AEs will be reviewed by a clinical development manager. The signs and events will be coded according to the MedDRA Dictionary for Adverse Reaction Terminology. The percentages of subjects with unsolicited AEs within 31 days after vaccination (Days 0-30) and the exact 95% CIs will be tabulated by vaccine group and by MedDRA preferred term. Similar tabulations will be done for Grade 3 unsolicited AEs, for unsolicited AEs possibly related to vaccination and for Grade 3 unsolicited AEs possibly related to vaccination.

The number and percentage of subjects who reported SAEs and new-onset chronic illness from administration of the booster vaccine dose until the end of the study will be tabulated with exact 95% CI.

SAEs and large injection site reactions will be described in detail.

The percentage of subjects using concomitant medication (any medication, any antipyretic/analgesic, any antipyretic/analgesic taken prophylactically, respectively) during the 4-day and 31-day follow-up periods (Days 0-3 and Days 0-30, respectively) after vaccination will be summarized.

MenACWY-TT-100 (C0921004)

Listings will be compiled for:

- Solicited local events
- Solicited general events

for the time interval from the booster vaccination until Day 4 after booster

Pregnancies

for the time interval from the booster vaccination until Day 31 after booster

- All SAEs
- AEs/SAEs leading to withdrawal
- SAEs related to study vaccination or any event related to lack of vaccine efficacy
- SAEs related to study participation
- All unsolicited AEs

for the time interval from the booster vaccination until the end of study follow-up.

8. STATISTICAL CALCULATIONS

8.1. Derived and Transformed Data

- Age in years will be calculated as (date minus date of birth)/365.25, rounded down to nearest integer.
- Duration from primary vaccination to any persistence time point will use day of primary vaccination as Day 0. Duration from booster will use day of booster vaccination as Day 0.
- Activity date is defined as the date associated with any activity performed at indicated visit.
- For a given subject and a given immunogenicity measurement, missing or non-evaluable measurements will not be replaced. Therefore, an analysis will exclude subjects with missing or non-evaluable measurements.
- The cutoff values for the assays are defined by the laboratory before the analysis and are described in Section 5.7.3 of the protocol.

MenACWY-TT-100 (C0921004)

- A seronegative subject is a subject whose titer is below the cutoff value.
- A seropositive subject is a subject whose titer is greater than or equal to the cutoff value.
- GMTs are calculated by taking the antilog of the mean of the log titer transformations. Antibody titers below the cutoff value of the assay will be given an arbitrary value of half the cutoff value for the purpose of the GMT calculation.
- rSBA vaccine response for groups A, C, W-135, and Y after the booster dose is defined as:
 - For initially seronegative subjects (pre-vaccination titer <1:8): rSBA antibody titers ≥1:32 1 month after vaccination, and
 - For initially seropositive subjects (pre-vaccination titer ≥1:8): a 4-fold increase in rSBA antibody titers 1 month after vaccination.
- hSBA vaccine response for groups A, C, W-135, and Y after the booster dose is defined as:
 - For initially seronegative subjects (pre-vaccination hSBA titer <1:4): hSBA antibody titers ≥1:8 1 month after vaccination, and
 - For initially seropositive subjects (pre-vaccination hSBA titer ≥1:4): a 4-fold increase in hSBA antibody titers 1 month after vaccination.
- For subjects who received MenC vaccine because they were suboptimal responders during the persistence phase of the MenACWY-TT-027 study, all subsequent persistence results for MenC will be replaced by half the cutoff in order to reflect the immunogenicity of the subjects, had they not been revaccinated. This includes Month 126. However, there will be no adjustment to postbooster MenC titers.
- For a given subject and the analysis of solicited events within 4 days after vaccination, missing or non-evaluable measurements will not be replaced. Therefore the analysis of the solicited events based on the total vaccinated cohort will include only vaccinated subjects for doses with documented safety data (ie, event screen completed). More specifically the following rules will be used:
 - Subjects who documented the absence of a solicited event after 1 dose will be considered not having that event after that dose.

MenACWY-TT-100 (C0921004)

- Subjects who documented the presence of a solicited event and fully or partially recorded daily measurement over the solicited period will be included in the summaries at that dose and classified according to their maximum observed daily recording over the solicited period.
- Subjects who documented the presence of a solicited event after 1 dose without having recorded any daily measurement will be assigned to the lowest intensity category at that dose (ie, 37.5°C for fever or Grade 1 for other events).
- Doses without event sheets documented will be excluded.
- All solicited local injection site events will be assigned a causal relationship to vaccination. Causal relationships of solicited general events were determined by the investigator.
- For the analysis, oral/axillary/tympanic temperatures will be coded as follows:

Grade	Temperature
0	<37.5°C
1	≥37.5°C - ≤38.5°C
2	>38.5°C - ≤39.5°C
3	>39.5°C

When temperature is measured by the rectal route, the corresponding oral temperature will be derived by subtracting 0.5°C from the temperature recorded. The above intensity grade will be applied to the derived oral temperature.

[figure not shown]
- Since subjects with fever will be counted once for each reported route, some subjects may be counted more than once.
- Intensity scales for other solicited general and local events are described in Section 8.2.3.2.1 of the protocol.
- For analysis of unsolicited AEs, such as SAEs or AEs by primary MedDRA term, and
 for the analysis of concomitant medications, all vaccinated subjects will be
 considered. Subjects who did not report the AE or the concomitant medication will
 be considered as subjects without the AE or the concomitant medication respectively.
- The day of onset for any SAEs reported from last persistence time point to Month 126 will be calculated as number of days since primary vaccination in Study MenACWY-TT-027.

MenACWY-TT-100 (C0921004)

• The way the percentage of subjects will be derived will depend on the event analysed (see table below for details). As a result, the N value will differ from one table to another.

Event	N used for Deriving % per Vaccine Group
Solicited general event	All subjects with at least 1 solicited general event documented as either present or absent (ie, event screen completed).
Solicited local event	All subjects with at least 1 solicited local event documented as either present or absent (ie, event screen completed).
Unsolicited AE	All subjects with study vaccine administered
Concomitant medication	All subjects with study vaccine administered

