4.3. Exclusion criteria for enrolment

Deviations from exclusion criteria are not allowed because they can potentially jeopardize the scientific integrity of the study, regulatory acceptability or subject safety. Therefore, adherence to the criteria as specified in the protocol is essential.

The following criteria should be checked at the time of study entry. If ANY exclusion criterion applies, the subject must not be included in the study:

Exclusion criteria for study entry

- Child in care
 - Please refer to the glossary of terms for the definition of child in care.
- Previous vaccination with meningococcal polysaccharide or conjugate vaccine outside of study MenACWY-TT-027.
 - Note: Subjects who were revaccinated with a monovalent MenC conjugate vaccine because of suboptimal response during the persistence phase of the MenACWY-TT-027 study (i.e. MenACWY-TT-028, -029, -030, -031 and -032) are allowed to participate as they will be followed for the persistence of MenA, MenW-135 and MenY.
- History of meningococcal disease due to serogroup A, C, W-135 or Y.
- Previous vaccination with meningococcal B vaccine.
- Any confirmed or suspected immunosuppressive or immunodeficient condition (congenital or secondary), including Human Immunodeficiency Virus (HIV) infection, based on medical history and physical examination (no laboratory testing required).
- Family history of congenital or hereditary immunodeficiency.
- Major congenital defects or serious chronic illness.
- History of chronic alcohol consumption and/or drug abuse.
- Subjects who withdrew consent to be contacted for follow-up studies

Additional exclusion criteria for booster phase at Month 126 study entry (to be checked at Month 126) for all subjects

36

- Use of any investigational or non-registered product (drug or vaccine) other than the study vaccine within 30 days preceding the booster dose of study vaccine, or planned use during the follow-up period.
- Administration of a vaccine not foreseen by the study protocol in the period starting 30 days before the booster dose of study vaccine or planned administration within 30 days after vaccination, with the exception of a licensed inactivated influenza vaccine.

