Recording of all SAEs8,12					•	•	•
Recording of serious adverse	•	•	•	•	•	•	•
events (SAEs) related to study							
vaccination and any event							
related to lack of vaccine efficacy							
since the previous visit.8,9							
Recording of SAEs related to	•	•	•	•	•	•	•
study participation ¹⁰							

Visit	VISIT 1*	VISIT 2*	VISIT 3*	VISIT 4*	VISIT 5*	VISIT 6 *	Phone Contact
Timing	Month 78 (Year 6)	Month 90 (Year 7)	Month 102 (Year 8)	Month 114 (Year 9)	Month 126 (Year 10)	Month 127	Month 132
Epoch	Epoch 001	Epoch 002	Epoch 003	Еросн 004		Epoch 005	
Recording of new onset of chronic illness (NOCI) ^{11,13}					•	•	•
Recording of Guillain Barré Syndrome (GBS) ^{12,13}					•	•	•
Recording of pregnancies ¹⁴					•	•	
Study Conclusion							● 15

Note: the double-line border following Months 78, 90, 102, 114, 127 and 132 indicates the analysis which will be performed on as clean as possible data obtained up to those time points.

ESFU: Extended Safety Follow-Up

• is used to indicate a study procedure that requires documentation in the individual eCRF.

O is used to indicate a study procedure to be captured in site source records that does not require documentation in the individual eCRF.

- *Subjects/subject's parent(s)/LAR(s) will be contacted by phone 4-8 weeks beforehand to come in for the persistence visit. The subject may return at any visit during the persistence epochs.
- ¹ Informed consent is only required at Visit 2, Visit 3, Visit 4 or Visit 5 if the informed consent form was not signed at previous study visits, i.e. if either Visit 2, Visit 3, Visit 4 or Visit 5 is the first persistence visit for a given subject. Subjects will be able to participate in any study visit 1, 2, 3, 4, or 5 independent of other study visits, at their own or at their parent/LAR's discretion as applicable (e.g., it is possible that a subject comes to Visit 1 and Visit 3 but not Visit 2).
- ² Check of inclusion and exclusion criteria for the persistence epochs at Visit 2, Visit 3, Visit 4 and Visit 5 is only required if these checks were not performed at a previous study visit, i.e. if Visit 2, Visit 3, Visit 4 or Visit 5 is the first persistence visit for a given subject.
- ³ Note that Visit 5 is part of the persistence epoch (Month 126: Visit 5) as well as the pre-booster vaccination visit. Thus if a subject first enters the study at Visit 5, eligibility criteria for both the persistence epoch and for the booster epoch will be checked.

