10.3. Determination of sample size

The actual sample size of this study with respect to the analysis of persistence and safety and immunogenicity post-booster is determined by a) the sample size of the primary vaccination study MenACWY-TT-027 (108658), b) by assumptions about the enrolment rate at the Year 6-10 extension study, and c) by assumptions about the annual dropout rate. All subjects who were vaccinated in study MenACWY-TT-027 (108658) and received either MenACWY-TT vaccine, *Meningitec* or *Mencevax ACWY* in study MenACWY-TT-027 (108658) will be eligible for this study if they meet the inclusion/exclusion criteria. Six hundred and thirteen subjects (460 in the ACWY-TT group and 75 in the MenCCRM group and 78 in the MenPS group) were enrolled and vaccinated in study MenACWY-TT-027 (108658). An enrollment rate equivalent to approximately 80% of the vaccinated population in study MenACWY-TT-027 (108658) is assumed, and an annual dropout rate of 10%.

If one assumes approximately 10% of subjects dropping out of the persistence study at every visit, then one expects the following numbers of subjects to participate at each persistence time point.

- For the analysis at Year 6, it is estimated that approximately 488 subjects will be enrolled (183 in the ACWY<2, 183 in the ACWY≥2 group, 61 in the MenCCRM group and 61 in the MenPS group)
- For the analysis at Year 7, it is estimated that approximately 440 subjects will be enrolled (165 in the ACWY<2, 165 in the ACWY≥2 group, 55 in the MenCCRM group and 55 in the MenPS group)

C0921004 (MenACWY-TT-100 EXT:027 Y6,7,8,9,10, 200171)
Protocol Amendment 2

- For the analysis at Year 8, it is estimated that approximately 400 subjects will be enrolled (150 in the ACWY<2, 150 in the ACWY≥2 group, 50 in the MenCCRM group and 50 in the MenPS group)
- For the analysis at Year 9, it is estimated that approximately 360 subjects will be enrolled (135 in the ACWY<2, 135 in the ACWY≥2 group, 45 in the MenCCRM group and 45 in the MenPS group)
- For the analysis at Year 10, it is estimated that approximately 326 subjects will be enrolled (122 in the ACWY<2, 122 in the ACWY≥2 group, 41 in the MenCCRM group and 41 in the MenPS group)

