6.2.1. Booster Total Vaccinated Cohort

The booster total vaccinated (BTV) cohort for safety will include all vaccinated subjects in the primary vaccination Study MenACWY-TT-027 (108658) with a documented booster vaccine administration.

For the analysis of immunogenicity after the booster vaccination the BTV cohort will include all subjects for whom data concerning post–booster immunogenicity endpoint measures are available.

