6.2.3. Booster ATP Cohort for Immunogenicity - MenC

The booster ATP cohort for immunogenicity – MenC will include all subjects who:

- are evaluable (ie, those meeting all eligibility criteria, complying with the procedures defined in the protocol and with no exclusion criteria during the study).
- are from the booster ATP cohort for safety.
- have assay results available for antibodies against MenC antigen for the blood sample taken 1 month post-vaccination, and

MenACWY-TT-100 (C0921004)

- were not administered a vaccine not foreseen by the study protocol from 30 days before the booster administration until the post-vaccination blood sample, and
- have not received a monovalent MenC conjugate vaccine or MenACWY conjugate vaccine because of suboptimal response to *N meningitidis* group C between the vaccination in the primary study (MenACWY-TT-027 [108568]) and the booster vaccine in this study, and
- have an interval between Visit 5 and Visit 6 of 21 to 48 days, inclusive.

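### In the conditional booster total vaccinated analysis, the half-cutoff Month 126 MenC value for revaccinees can only raise booster response and lower the pre-booster GMT, or leave them unchanged

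*SAP*

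**What the plan says.** - **Who is affected.** Protocol 4.3 lets subjects enter if they were given a monovalent MenC conjugate vaccine for suboptimal response during the earlier persistence studies. They "are allowed to participate as they will be followed for the persistence of MenA, MenW-135 and MenY".
- **The replacement.** SAP 8.1 sets all their later MenC persistence results to half the cutoff, to show where they would have stood without revaccination. On scope it says: "This includes Month 126. However, there will be no adjustment to postbooster MenC titers". The cutoffs are 1:8 for rSBA and 1:4 for hSBA (Protocol Table 7, Appendix A), so the replaced values are 4 and 2.
- **Month 126 has two roles.** Protocol Table 4, footnote 3: "Note that Visit 5 is part of the persistence epoch (Month 126: Visit 5) as well as the pre-booster vaccination visit". SAP 7.2.2.1 summarises booster results "For each vaccine group, at each blood sampling time point (Month 126 and Month 127), for each antigen assessed".
- **Main booster MenC analysis.** SAP 6.2.3 admits only subjects who "have not received a monovalent MenC conjugate vaccine or MenACWY conjugate vaccine because of suboptimal response to" serogroup C, so it contains no revaccinees.
- **Complementary analysis.** SAP 6.2.1 has no such exclusion: "For the analysis of immunogenicity after the booster vaccination the BTV cohort will include all subjects for whom data concerning" post-booster immunogenicity are available. SAP 7.2.2 says that, when more than 10% of subjects with serology in any vaccine group are outside the booster ATP cohort, "a second analysis based on the booster total vaccinated cohort will be performed to complement the booster ATP analysis".

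**The concern.** The replacement answers a persistence question: what would MenC antibody have been without the extra dose? SAP section 10 justifies it on that ground, because dropping these subjects would overstate MenC persistence. Booster response is a different quantity, a within-subject change from Month 126 to Month 127. Taking the first value from a hypothetical history and the second from the real one estimates neither the observed response nor the response of a subject who was never revaccinated. A revaccinee with rSBA 1:256 before and 1:256 after the booster would be counted as a responder.

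The BTV analysis exists to show whether the ATP result depends on exclusions. If its MenC response is higher and its pre-booster GMT lower partly because of a derivation rule, a reader could take that for a real difference between cohorts.

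**Working it through.** The plan gives no figure for the effect of this rule, so there is none to reproduce. The steps below establish the direction, then bound the size.

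**1. Post-booster titre needed to be a responder (SAP 4.2 and 8.1)**

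| Assay | Measured pre-booster titre | Needed with measured pre | Needed with replaced pre |
|---|---|---|---|
| rSBA | below 8 | at least 32 | at least 32 |
| rSBA | 8 or higher | at least 4 × pre, so never below 4 × 8 = 32 | at least 32 |
| hSBA | below 4 | at least 8 | at least 8 |
| hSBA | 4 or higher | at least 4 × pre, so never below 4 × 4 = 16 | at least 8 |

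Replacement never raises the threshold. Status therefore stays the same or changes from non-responder to responder.

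- rSBA status changes when the measured pre titre is 1:16 or higher (on doubling dilutions) and the post titre is at least 1:32 but less than four times the pre titre. At a pre titre of exactly 1:8 both rules require 1:32, so nothing changes.
- hSBA status changes when the pre titre is at least 1:4 and the post titre is at least 1:8 but less than four times the pre titre.

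**2. Numerical check**

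Every pre/post pair was scored under both rules.

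| Doubling-dilution grid | Pairs | Become responder | Become non-responder | Unchanged |
|---|---|---|---|---|
| rSBA (<1:8, 1:8 to 1:32768) | 196 | 77 | 0 | 119 |
| hSBA (<1:4, 1:4 to 1:8192) | 169 | 77 | 0 | 92 |

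These count titre combinations, not expected subjects. One million random continuous pairs per assay also gave no change to non-responder. SAP 8.1 omits the words at least before 4-fold, which SAP 4.2 includes. Reading it as exactly four-fold still gives no change to non-responder.

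SAP 8.1 leaves missing titres missing, so the response denominator is the same under both rules.

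**3. Effect on the response percentage**

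The only sizes in the documents are the planned Year 10 numbers in Protocol 10.3: "122 in the ACWY<2, 122 in the ACWY≥2 group, 41 in the MenCCRM group and 41 in the MenPS group". Four years of 10% dropout give 183 × 0.9⁴ = 120.1 and 61 × 0.9⁴ = 40.0, close to the stated 122 and 41.

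- Per subject whose status changes: 1/122 = 0.82 points; 1/41 = 2.44 points.
- Smallest count above 10%: 13/122 = 10.7% (12/122 = 9.8%); 5/41 = 12.2% (4/41 = 9.8%). If revaccinees alone only just met the trigger, the rise would lie between 0 and 10.7 points, or between 0 and 12.2 points.
- In general, inflation = f × s, where f is the revaccinated share and s is the share of revaccinees whose status changes. Both are assumptions:

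| f | s = 0 | s = 0.063 | s = 0.30 | s = 0.70 |
|---|---|---|---|---|
| 5% | 0 | 0.3 | 1.5 | 3.5 points |
| 10% | 0 | 0.6 | 3.0 | 7.0 points |

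The low value of s stands for the case where nearly all revaccinees rise four-fold anyway, or were already low at Month 126.

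**4. Effect on the Month 126 GMT**

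Replacing the revaccinees' rSBA titres (measured GMT T) by 4 changes the mean log titre by f × log(4/T). So reported GMT = measured GMT × (4/T)^f, whatever the other subjects' titres. Half the cutoff is the lowest value the GMT calculation allows, so T is at least 4 and the factor is at most 1.

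| T (assumed) | f = 5% | f = 10% |
|---|---|---|
| 4 (all below 1:8) | 1.00 | 1.00 |
| 32 | 0.90 | 0.81 |
| 256 | 0.81 | 0.66 |

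The Month 126 percentages at or above 1:8 and 1:128 (rSBA), and 1:4 and 1:8 (hSBA), likewise fall or stay the same, because the replaced value is below every threshold.

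**The case against.** **The rule may cover persistence tables only.** SAP 8.1 speaks of persistence results, SAP 6.1.3 lists Month 126 among the persistence time points, and the rationale in section 10 concerns persistence. Nothing says outright that the replaced value is the baseline for booster response. This reading is possible but strained. SAP 8.1 names Month 126 and then exempts only the post-booster titres, which reads as a rule on the data, and SAP 7.2.2 does not restore the measured value. If the narrow reading was meant, the fix records it.

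**Little depends on it.** The BTV analysis must be triggered, revaccinees must have been boosted and bled, and their titres must fall in the ranges above. All analyses are descriptive, the booster phase is uncontrolled, and the primary endpoints are rSBA persistence. This stands and limits the importance of the point. SAP 7.2.2 also does not say whether the 10% rule refers to the MenC or the MenAWY booster cohort. That affects whether the analysis runs, not the direction of the effect.

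**The scenarios are assumed.** This also stands. Only the per-subject increments and the trigger counts follow from document figures, and those use planned rather than observed numbers.

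**Measured titres would not make the two cohorts comparable.** True: revaccinees had an additional MenC dose, so BTV and ATP could still differ. But that would be a real difference between the cohorts. The half-cutoff rule adds an artificial one.

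**Conclusion.** The concern holds. As written, SAP 8.1 pairs a hypothetical Month 126 value with a real Month 127 value for every MenC revaccinee in the BTV cohort. If that analysis runs, MenC booster response is biased upward or unchanged, and Month 126 MenC GMT and percentages are biased downward or unchanged, for both assays. The booster ATP MenC result and the measured Month 127 titres are not affected.

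The direction rests only on the response definitions, the half-cutoff floor and the rule that missing titres stay missing. The size cannot be determined from the documents. It is zero if the BTV cohort has no revaccinees or if all of them are already below the cutoff at Month 126. The shares, change rates and titres in the scenarios are assumptions. This is a fault in a secondary, conditional analysis that should be corrected; it does not threaten the primary results.

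**What to change.** - State in SAP 8.1 and 7.2.2 that the half-cutoff replacement applies to the persistence analyses only.
- In all post-booster analyses, use the measured Month 126 MenC titre for booster response, pre-booster GMT and percentages above the thresholds.
- Add a footnote explaining why Month 126 MenC values differ between the persistence tables and the BTV booster tables.

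The cost is one SAP sentence, one derivation flag and one table footnote. The values being replaced are measured results, so no new data or assays are needed.

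### SAP 8.1 gives all solicited symptoms of a class one denominator, so a symptom left blank on an otherwise documented screen can only count as absent; N should be set per symptom

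*SAP*

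**What the plan says.** SAP 7.2.3 (Analysis of Post-booster Safety) plans symptom-by-symptom output with exact 95% confidence intervals over Days 0-3: "The numbers and percentages of subjects reporting each solicited local (any grade, Grade 3, medical advice"), and likewise for each general event.

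The table at the end of SAP 8.1 sets the denominators by class. For general events N is "All subjects with at least 1 solicited general event documented as either present or absent (ie, event screen completed"). For local events it is "All subjects with at least 1 solicited local event documented as either present or absent (ie, event screen completed"). No N is defined for an individual symptom.

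Earlier in SAP 8.1 the missing-data rules begin: "For a given subject and the analysis of solicited events within 4 days after vaccination, missing or non-evaluable measurements will not be replaced". The SAP then draws the consequence that the analysis "will include only vaccinated subjects for doses with documented safety data (ie, event screen completed"). It adds three further rules that matter here:

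- "Subjects who documented the absence of a solicited event after 1 dose will be considered not having that event after that dose".
- A subject who documents that a symptom was present but records no daily value is given the lowest intensity category, and so counts as having had it.
- "Doses without event sheets documented will be excluded".

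Treating non-report as absence is stated in SAP 8.1 only for unsolicited adverse events and concomitant medication.

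**The concern.** The rule for counting a subject as free of a symptom is specific to that symptom and requires documented absence. The denominator is not symptom-specific: one documented symptom of the class admits the subject for all of them. There are four general symptoms (Protocol 8.1.6.2) and three local ones (Protocol 8.1.6.1). A subject who answers for headache and leaves the fever item blank enters the fever denominator with no route into the numerator, so blank has become absent.

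Solicited symptoms after the booster are a secondary endpoint (Protocol 10.2, SAP 5.2). If items are left blank, the symptom percentages take the lowest value that the data allow, and their intervals are computed on more subjects than were assessed.

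**Working it through.** **Nothing to reproduce directly.** The documents give no expected reactogenicity rate and no item-level missing rate. The interval method can be checked: SAP 8.3.1 specifies Clopper-Pearson, and the Year 10 rows of Protocol Table 17 reproduce with it (24/122 gives 13.0 to 27.8; 8/41 gives 8.8 to 34.9).

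**Step 1: trace the possible records for one symptom (fever), with another general symptom documented except where stated.**

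| Record | Rule in SAP 8.1 | In N | In numerator |
|---|---|---|---|
| Absence documented | Counted as not having it | Yes | No |
| Presence documented, some or all temperatures recorded | Graded by maximum | Yes | Yes |
| Presence documented, no temperature | Lowest category (37.5°C) | Yes | Yes |
| No event sheet at all | Excluded | No | No |
| Fever item blank, headache documented | None stated | Yes, on a literal reading | No |

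Only the last row is at issue. The same tracing applies to redness or swelling when pain is documented. The two classes are separate, so a local entry does not bring a subject into the fever denominator.

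**Step 2: formula.** Let N be the class-level denominator, m the share of N with this symptom undocumented, M = N(1 - m) the number assessed, and x the number with the symptom. Then

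reported rate = x/N = (x/M)(1 - m).

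**Step 3: numbers.** m is an assumption, shown over a range.

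| Available-case rate x/M | m = 0 | 1% | 5% | 10% | 20% |
|---|---|---|---|---|---|
| 10% | 10.0 | 9.9 | 9.5 | 9.0 | 8.0 |
| 40% | 40.0 | 39.6 | 38.0 | 36.0 | 32.0 |

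**Step 4: whole-number examples at the planned Year 10 group sizes** (122 and 41, Protocol 10.3), assuming that all of these subjects are boosted and have some symptom of the class documented.

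| N | Blank for this symptom | With class-level N | With symptom-specific N | If every blank were an event |
|---|---|---|---|---|
| 122 | 12 | 11/122 = 9.0% (4.6 to 15.6) | 11/110 = 10.0% (5.1 to 17.2) | 23/122 = 18.9% |
| 41 | 4 | 4/41 = 9.8% (2.7 to 23.1) | 4/37 = 10.8% (3.0 to 25.4) | 8/41 = 19.5% |

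The estimate moves by about 1 point. The interval is 11.0 points wide instead of 12.1 in the first example (15.6 - 4.6 against 17.2 - 5.1), and 20.4 instead of 22.4 in the second (23.1 - 2.7 against 25.4 - 3.0). The class-level figure is the lower bound: every blank is scored as event-free.

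**The case against.** The strongest reply is that the SAP is consistent with itself. It turns the no-replacement principle into a screen-level inclusion rule, and the denominator table repeats the same parenthetical about a completed screen. Nothing says that a screen with a blank item counts as completed, or that a blank is scored as absent. This stands in part: the problem is an unresolved ambiguity, not a flat contradiction. But the threshold in the table is one documented symptom, and that wording would serve no purpose if completion meant that every symptom was answered.

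A reader might infer that anyone without a temperature reading is counted as afebrile. The documents do not support that. Presence or absence is recorded separately from the daily value, and presence without a value still counts as an event. Only a blank present/absent entry is affected.

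Blanks may also be few. The investigator verifies the diary card with the subject or parent at Visit 6 (Protocol 5.6.15), and eCRF omissions can be queried (Protocol 11.1). That stands, and m may be near zero.

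The available-case rate is not necessarily the true rate. If subjects tend to leave blank the symptoms that they did not have, a symptom-specific N would overstate incidence. That also stands, and is a reason to print the number assessed on each row.

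Finally, the table layouts are in an annex to the SAP that is not among the documents. They may already show N per row, but they would not change the rule in SAP 8.1 unless they redefine N.

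**Conclusion.** The point holds as a gap in the denominator rule. Read literally, SAP 8.1 scores a blank individual symptom as absent whenever another symptom of the same class is documented, and the SAP states no rule that says it should. Relative to the available-case rate, the percentage falls by the fraction m. At an assumed m of 1% to 10%, a 10% rate becomes 9.9% to 9.0%, well inside the exact interval for groups of 122 or 41. With no blanks there is no effect.

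A reader might conclude that booster reactogenicity is in fact biased downward. The documents do not establish this: they give no item-level missing rate, and they do not show that the available-case rate is the right benchmark. For fever even the net direction is open, because a separate rule in SAP 8.1 counts a febrile subject once for each reported measurement route, which can raise the count.

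The priority is low. The booster phase is uncontrolled (Protocol 3), all analyses are descriptive (Protocol 10.6), and no threshold or test depends on this N.

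**What to change.** In the SAP 8.1 table of denominators:

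- For each individual solicited symptom, set N to the subjects with that symptom documented as present or absent on Days 0-3. For fever, count a subject as documented if a temperature was recorded or fever was marked present or absent.
- Keep the class-level N only for the any-local and any-general summary rows.
- Print N on every symptom row.

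The cost is one line in the SAP and a change to the table program. The downside is that N will vary by row within a table and some rates may be slightly higher.
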